13.2. Financing plan

14. TIME SCHEDULE AND PUBLICATION PLAN

14.1. Time schedule

14.2 Publication plan

15. STUDY ORGANIZATION

16. REFERENCES

1. STUDY SYNOPSIS: NCP – Autologous Chondrocyte Implantation

Topic	Details
Protocol Title:	Focal cartilage defects in the knee – A randomized controlled trial comparing Autologous Chondrocyte Implantation with arthroscopic debridement
Study Type:	Clinical
Indication:	Compare the effect of Autologous Chondrocyte Implantation (ACI) with arthroscopic debridement (AD) in patients with symptomatic full thickness knee cartilage injuries larger than 2cm ² .
Hypothesis Statement	
Focal cartilage injuries in the knee might have devastating effect both in the short term and in the long term. Various surgical treatment options are available; with ACI established as a recognized treatment method for larger lesions. Meta-analysis and systematic reviews have required well-designed, long-term, multicenter studies to evaluate clinical outcomes of ACI with the use of a “no treatment” group as a control group.
 
H0: There is no difference in KOOS QoL after ACI or AD from baseline to 24 months after surgery.
 
H1: There is a difference in KOOS QoL after ACI or AD from baseline to 24 months after surgery.

Study Objectives:	
Questionnaires: KOOS, Tegner score, Lysholm score, EQ-5D, VAS.
 
Physical examination: range of motion and hop test.
 
Radiology: x-ray and MRI of the knee.
 
Primary aim: KOOS quality of life (QoL) subscore.

Study Design:	Prospective, single-blinded parallel-group bicenter study with 2 treatment arms.
Duration of Study Participation:	Approx. 36 months inclusion and 24 months follow up. In total 5 years.
Follow-up Period:	24 months. All will be invited to participate in late controls after 5 and 10 years.
Study Location:	2 Norwegian hospitals: Akershus University Hospital and Oslo University Hospital – Ullevål.
Number of Planned Subjects:	82 patients
Study Population:	Inclusion: age 18-50 years old, single symptomatic cartilage defect on femoral condyle or trochlea, defect size larger than 2

	cm2, defect ICRS grade 3-4, ligamentous stable knee, range of motion 5-105°, Lysholm score < 75 and informed consent. Exclusion: Osteoarthritis, rheumatoid or other systemic arthritis, malalignment > 5° measured on x-rays, BMI > 30, comorbidities that may influence surgery or rehabilitation, pregnancy, inability to complete questionnaires or rehabilitation, serious alcohol or drug abuse, previous cartilage surgery to the chondral defect except OCD surgery.
Treatment Groups:	2 treatment groups with 41 patients in each group.
Visit Schedule:	3 months (\pm 2 weeks), 6 months (\pm 4 weeks), 12 months (\pm 6 weeks) and 24 months (\pm 8 weeks). All will be invited to participate in late controls after 5 and 10 years.
Safety Assessments:	If any unforeseen complication outside normal clinical practice occurs, the sponsor representative will be contacted as soon as possible with a parallel message to the local coordinators at the involved hospitals. During each follow up, there will be a case report form (CRF) regarding complications and safety.
Sample Collection:	A 5 mL venous blood sample will be drawn on the day of operation. The blood sample will be centrifuged before serum is pipetted in a sterile tube. The serum will be analyzed at Oslo University Hospital – Rikshospitalet on the cartilage biomarker microRNA-140 (miR-140). During the open chondrocyte implantation the excess cartilage debrided from the rim of the lesion will be sent for similar microRNA-140 (miR-140) analysis. (applicable for the 41 patients in the ACI arm only)
Overview of Statistical Plan:	If normal distribution, aims will be analyzed using linear mixed models (LMM), and the primary aim will be performed as a post hoc test for the LMM, similar to performing a two-sample t-test. If no normal distribution, analysis will be performed using Mann-Whitney U-test.
Sample Size Determination:	Detecting a difference of 10 in primary aim with 80% power using a standard deviation of 15. A $p < 0,05$ is statistically significant.

Interim Analysis:	This gives 37 patients in each group, adding 10% drop out meaning 41 patients in each group and 82 in total.
Ongoing Data Monitoring Plan:	No interim analysis will be done.
Study Stopping Rules:	Monitor at Akershus University Hospital.
End of Study:	Inclusion of 82 patients.
Operational Risk Analysis:	The end of this study is 24 months after the last included patient.
Study Target Dates:	Inability to include 82 patients in 3 years. May prolong the inclusion period, or add other including hospitals in the study.
	See table below.

Milestone	Study Timeline: Target Date (Month/Year)
IND Submitted (if appropriate)	October 2015
First Patient In (FPI)	March 2016
Last Patient In (LPI)	March 2019
Last Patient Out (LPO)	March 2021
Database Lock (DBL)	April 2021
First Look (FL)	May 2021
CSR Completed	December 2021

Tests and assessments	Inclusion	Surgery	3 months	6 months	12 months	24 months
Medical History	X		X	X	X	X
Physical Examination	X		X	X	X	X
Questionnaires	X		X	X	X	X
X-ray	X					X
Informed Consent	X					
Randomization and surgery		X				
Serum and cartilage sample		X				
MRI						X
Adverse Events			Monitor and record throughout the study			

Study Activities

2. SHORT SUMMARY

Focal cartilage injuries in the knee might have devastating effect both in the short term and in the long term due to the predisposition of early onset osteoarthritis. To this date, various surgical treatment options are available. Since its introduction in the late 1980s, autologous chondrocyte implantation has become a recognized treatment option for larger cartilage lesions in the knee. In this study we want to increase clinical and economic knowledge about autologous chondrocyte implantation compared to arthroscopic debridement in the short and long run.

3. INTRODUCTION

3.1. Background

The articular surfaces of joints are covered with hyaline cartilage, a unique tissue with extreme load shearing and low-friction properties. However, these characteristics come with a cost. It is aneural and avascular which explains its limited ability to self-repair[1-3]. Damage to the cartilage, which is common in young active adults, will therefore lead to permanent damage. These injuries are very common, with a reported prevalence of 12 % in the population [4]. Focal cartilage lesions predispose to development of early onset osteoarthritis, which in turn may lead to long rehabilitation periods and loss of function and time off work. Musculoskeletal problems are one of the major reasons for workers compensation and especially for younger patients this may lead to a significant reduced quality of life and loss of income [5-8]. Treatment of symptomatic cartilage injuries in the knee is therefore of particular interest and importance to the patient, the surgeon and the society [3, 9, 10].

The ideal treatment for isolated cartilage injuries aims at recreating a healthy hyaline-type tissue with similar strength and durability as the normal cartilage in the rest of the joint. Current surgical treatment options include debridement, microfracture, autologous osteochondral transplantation (mosaicplasty) and autologous chondrocyte implantation (ACI) [11-13]. Several studies conclude that microfracture is not effective for larger lesions [26, 27]. The purpose of arthroscopic debridement is to remove loose intraarticular tissue debris and inflammatory mediators down to the subchondral bone, but not through it [12]. ACI attempts to re-implant the patient's own chondrocytes over the defect to permit the chondrocytes to heal back onto the bone and mature into a hyaline-like cartilage. ACI have been directly compared to microfracture and mosaicplasty in randomized controlled trials [20, 35, 36]. The results indicate improved knee function in (carefully selected) patients [14], but studies have been criticized for methodological weaknesses [15]. The Cochrane database reported that there is insufficient evidence to conclude that ACI is superior to other treatment strategies for treating full thickness cartilage defect of the knee [19].

No statistically significant differences have been found between the different surgical treatments. This supports the suggestion that the improvement might be a result of the post-operative rehabilitation rather than the surgery itself [16, 17]. Furthermore, inclusion in a clinical trial is known to improve symptoms by itself, known as the Hawthorne effect [18].

All studies on cartilage reconstructive surgery have put the patients through a strict, careful, intensive and prolonged rehabilitation following the procedure, which could contribute to the clinical improvement observed. Wondrasch and co-workers implemented an active rehabilitation program in 48 patients with focal cartilage damage to a weight-bearing area of the knee [17]. None of the patients had any form of surgery to their injury. After three months there was a statistical significant and clinical meaningful improvement in KOOS score, load progression and hop score, to the point where 31 (65%) of the patients declined further surgery for their cartilage lesion. This indicates that good results can be achieved with physiotherapy alone. Dozin and coworkers compared ACI versus mosaicplasty, where all candidates were evaluated arthroscopically with debridement of the lesion 6 months prior to definitive treatment [20]. All candidates completed an intensive rehabilitation protocol following the debridement, but before the cartilage surgery. This included non-weight bearing for two weeks and immediate active and passive physiotherapy. After two weeks isometric and proprioception exercises were introduced, as well as gradually strengthening exercises. 31 % of the candidates experienced substantial clinical improvement following the debridement and physiotherapy alone, and needed no further (surgical) treatment, questioning the need for cartilage treatment as a first port of call in such patients. The authors conclude that further randomized clinical trials are needed, where ACI should be compared to debridement alone. This is a missing link in our knowledge of cartilage reconstructive surgery and hampers further progression in cell therapy [20,33].

3.2. Purpose of this study

The purpose of this trial is to compare autologous chondrocyte implantation (ACI) with arthroscopic debridement (AD) in symptomatic cartilage injuries larger than 2 cm² in patients aged 18-50 years old in regard to both subjective and objective variables at predefined times as described under “variables” in section 6.

4. RESEARCH DESIGN

The study is part of “The Norwegian Cartilage Project (NCP): A multidisciplinary Approach to Improve the Treatment of Injured Articular Cartilage”, which is a total of five studies regarding cartilage injuries in the knee, including clinical trials, register studies and basic research studies.

This study is a prospective, randomized, controlled study with 2 treatment arms (ACI and AD). The study will be conducted at Akershus University Hospital and Oslo University Hospital with multicenter inclusion contribution from other Norwegian institutions which together form the NCP network of hospitals: These hospitals are in addition to Akershus and Oslo University Hospitals: Kristiansund Hospital, Haukeland University Hospital, Ålesund Hospital, Diakonhjemmet Hospital and Buskerud Hospital.

Because one treatment arm consists of a two stage surgery, with a mini-open arthrotomy, while the other treatment arm is a single stage arthroscopy, it will not be possible to blind the patients as to what treatment they have received.

Inclusion and treatment will take place at Akershus University Hospital (Ahus) or Oslo University Hospital (Ullevål). The follow up appointments will be performed at Ahus or at the local NCP affiliated hospital by an external reviewer connected to the NCP group. The follow up will be blinded so that the examiner is unaware of which treatment arm the patient belongs to. To achieve this, the patient is instructed not to reveal the nature of the treatment he/she has received, and an opaque elastic stocking is put over the knee to conceal the scars (which are different between the treatments). Follow up is planned to 2 years, but each participant will also be invited to clinical and radiological follow ups after 5 and 10 years.

[figure not shown]
4.1. Participants

The study will include a total of 82 patients, both men and non-pregnant women, with a full thickness or osteochondral defect in the weight bearing area of the femoral condyles or trochlea larger than 2 cm². The lesion must be symptomatic, with a Lysholm score less than 75 [34]. The inclusion criteria are based on the recommendations by Brittberg [22], and include patients aged 18 to 50 years old with a stable knee, good range of motion (ROM), normal alignment (less than 5° varus or valgus measured on hip-knee-ankle (HKA) angle images) and no sign of radiologically osteoarthritis classified after Kellgren-Lawrence [37]. The weight-bearing, fixed-flexion posteroanterior radiographs will be obtained with the SynaFlex X-ray positioning frame (Synarc) [38].

5. MATERIALS AND METHODS

All patients will be assessed clinically as well as radiologically prior to inclusion to avoid peroperative exclusions. The full thickness or osteochondral defect will be verified arthroscopically as a grade 3 or 4 lesion according to the International Cartilage Repair Society (ICRS) [39]. Still, some patients might not be included peroperatively based on arthroscopic findings such as osteoarthritis, less than 50% normal meniscus or inappropriate size of the lesion [40]. The definitive inclusion of the patient will be performed by the operating surgeon during the diagnostic arthroscopy, prior to randomization. Patients who will be excluded based on peroperative findings will receive appropriate treatment according to the standard of care at the local hospitals.

Exclusion criteria include general osteoarthritis, systemic arthritis, severe co-morbidities that may influence surgery or rehabilitation potential, significant alcohol or drug abuse, psychiatric disorders, language barriers, pregnancy, severe obesity (body mass index > 30) and previous surgery to the chondral defect such as previous microfracture (previous cruciate ligament reconstruction, fixation of osteochondritis dissecans lesions, alignment procedures (osteotomies) or meniscal surgeries are not exclusion criteria). Patients declining participation in the trial (and who fulfill the inclusion criteria) or withdrawing underway will receive appropriate treatment according to the standard of care at the local hospital.

The participants will also receive information about a parallel study (Healer Non-healer study) regarding obtaining venous blood samples, which also is part of the Norwegian Cartilage Project. For more information, see “Operative procedure – blood samples for parallel study” in section 5.4 and “Additional and secondary projects” in section 8.2.

Inclusion criteria	Exclusion criteria

 -Age 18-50 years old -Single symptomatic cartilage defect on medial or lateral femoral condyle or trochlea -Defect size larger than 2 cm² -Lesion graded ICRS 3-4 ->50% intact meniscus -Ligamentous stable knee -Acceptable range of motion (5-105°) -Lysholm score < 75 -Informed consent 	
 -Osteoarthritis, rheumatoid or other systemic arthritis -Malalignment >5° measured on HKA images -No radiological osteoarthritis -Obesity (Body mass index > 30) -Comorbidities that may influence surgery or rehabilitation -Pregnancy -Inability to complete questionnaires or rehabilitation -Serious alcohol or drug abuse -Previous surgery to the chondral defect except OCD surgery

Inclusion and exclusion criteria

5.2. Randomization

The randomisation will be performed using an computer generator (randomization.org). 82 patient will be block randomized in pairs of six-eight (1:1) to treatment allocations. Each patient receives a patient number (1 through 82) on inclusion. Randomization will be printed in faded text and concealed in opaque numerically marked envelopes. The printing and concealing will be done by a person working at Akershus University Hospital, but is not involved in the study, to secure blinding. The randomization process occurs in the operation theatre during the arthroscopy after the operating surgeon has measured and graded the lesion to fulfill the inclusion criteria (see section “4.3 Operative procedure”).

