All the operating surgeons will receive proper training in the operative procedure before study start.

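### Section 5.2 describes one 1–82 envelope series with no hospital stratum for a trial said to operate at two hospitals, so arm balance within each hospital is left to chance: a small loss of precision, not a bias

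*Protocol*

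**What the plan says.** **Randomisation (section 5.2).** "82 patient will be block randomized in pairs of six-eight (1:1) to treatment allocations". Numbering is a single run: "Each patient receives a patient number (1 through 82) on inclusion". The printed allocations are "concealed in opaque numerically marked envelopes", prepared by an uninvolved Ahus employee. "The randomization process occurs in the operation theatre during the arthroscopy", once the surgeon has measured and graded the lesion. The section names no stratification factor and no list or envelope set per hospital. It does not say how numbers are issued when two theatres draw on the series.

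**Hospitals.** The synopsis (section 1) labels the trial "Prospective, single-blinded parallel-group bicenter study with 2 treatment arms". Section 4 says "Inclusion and treatment will take place at Akershus University Hospital (Ahus) or Oslo University Hospital (Ullevål"). If recruitment is slow, the synopsis allows more sites: "May prolong the inclusion period, or add other including hospitals in the study". Section 5.3 implies several surgeons ("All the operating surgeons will receive proper training in the operative procedure before study start") but gives neither their number nor their split by hospital.

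**A conflicting description.** The ACI part of section 5.3 names Ahus, with Oslo University Hospital appearing through its cell laboratory, and has the cultured cells returned to Ahus for implantation. Section 4 reads as if either hospital may treat.

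**Analysis (section 7.2).** The mixed model has time, group and their interaction. Age and lesion severity are given as examples of adjustment factors. Hospital and surgeon are not named, but the list is open-ended.

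**The concern.** Blocking guarantees near-equal arms only along the sequence to which it is applied. If one sequence is spread over two hospitals, the patients of each hospital are an arbitrary subset of it. The 41:41 balance then holds for the whole trial but not within either hospital.

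Both arms are surgical, so the operating hospital stands for surgeons and local practice that could affect KOOS QoL. If outcomes differ by hospital, a chance imbalance in hospital mix moves the unadjusted arm difference in that particular trial. What is at stake is precision and how convincing a result from 82 patients looks. The structure of the list has to be settled before the first envelope is opened: an analysis plan can add a hospital term later, but it cannot restore balance.

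**Working it through.** **1. The plan's own figures (sections 1 and 7.3).** Difference 10, SD of change 15, two-sided 5%, power 80%. The two-sample t-test calculation gives 36.31, rounded up to 37 per group. Adding 10%: 37 × 1.1 = 40.7, so 41 per group and 82 in total. This reproduces the plan. A list of 82 can be built from whole blocks of 6 and 8 (6a + 8b = 82 for (a, b) = (3, 8), (7, 5) or (11, 2)), so one list can end at exactly 41:41.

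**2. Balance within a hospital.** The protocol gives no split of patients between hospitals, so the share is an assumption and was varied. Simulation: 82 patients, randomly ordered blocks of 6 or 8, each patient falling to the smaller hospital with the stated probability, 8,000 runs per share. The gap is the absolute difference between the numbers of ACI and AD patients in the smaller hospital.

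| Smaller hospital's share (assumed) | One list: mean gap | One list: 95th percentile | One list: chance of gap ≥ 6 | List per hospital: 95th percentile (maximum) |
|---|---|---|---|---|
| 50% | 3.6 | 9 | 23.1% | 2 (4) |
| 40% | 3.6 | 9 | 21.8% | 2 (4) |
| 30% | 3.3 | 8 | 18.5% | 2 (4) |
| 20% | 2.9 | 7 | 12.7% | 2 (4) |
| 10% | 2.1 | 5 | 4.0% | 2 (4) |

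**3. Effect on the arm contrast.** With 41 per arm, a gap g makes the arms' hospital shares differ by g/41. If the hospitals differ by D points, the unadjusted contrast shifts by (g/41) × D. D is also an assumption. At the 95th-percentile gap with D = 5:

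- share 20%: 7/41 × 5 = 0.85
- share 30%: 8/41 × 5 = 0.98
- share 40% or 50%: 9/41 × 5 = 1.10

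With D = 10 these double, to about 1.7 to 2.2. At the mean gap with D = 5, shares of 20% to 50% give 2.9/41 × 5 = 0.35 to 3.6/41 × 5 = 0.44.

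**4. Yardstick.** The standard error of the arm difference is 15 × √(2/41) = 3.31. The shifts of 0.85 to 1.10 are 0.26 to 0.33 of a standard error, and about a tenth of the 10-point target.

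**5. What a hospital term would buy.** A difference of D between hospitals with shares p and 1 − p contributes D² × p(1 − p) to the variance. For D = 5 this is 25 × 0.16 = 4.0 at p = 20% and 25 × 0.25 = 6.25 at p = 50%. Out of 15² = 225 that is 1.8% to 2.8%, so adjustment would shorten the standard error by about 0.9% to 1.4%.

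**6. Price of separate lists in overall balance.** In the same simulation the 95th percentile of the overall arm gap was 2 to 4 patients. At 43:39 the standard error is 15 × √(1/43 + 1/39) = 3.32, against 3.31 at 41:41.

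**The case against.** The case for leaving section 5.2 alone is substantial.

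- **Unstratified blocking is valid.** A reader might infer that the comparison is biased or the test unsound. It is neither: hospital imbalance arises by chance, and ordinary random error already allows for it. This stands.
- **The size rests on assumptions.** Neither a hospital split nor a hospital difference is documented, and the typical shift is below half a point for an assumed 5-point difference. This stands, and it caps the importance of the point.
- **There may be only one operating hospital.** Section 5.3 can be read as placing ACI surgery at Ahus. If all surgery were there, the hospital argument would fall away. This stands as a condition, but section 4 and the synopsis say otherwise, so the passages must be reconciled.
- **Logistics.** One might infer that a single series cannot work in two theatres, or that it would be split in mid-block. The protocol does not support that. Numbers could be issued centrally, or whole blocks sent to each hospital. It simply does not say.
- **Follow-up.** One might infer that hospital also determines follow-up. Section 4 places follow-up at Ahus or at a local affiliated hospital with an examiner unaware of treatment, so follow-up site is not tied to the operating hospital. Blocking on the latter would not balance it.
- **The model term.** The absence of hospital from section 7.2 is not in itself an error, because the list of adjustment factors is only illustrative.
- **Separate lists have a cost.** The surgeon decides definitive inclusion during arthroscopy, just before randomisation, and learns each allocation. With a list per hospital each theatre sees its whole sequence, so block ends become easier to guess. This stands and belongs in the trade-off.

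**Conclusion.** The point holds as a minor improvement. On the natural reading of section 5.2 there is one series of 82 with no hospital stratum, so with two operating hospitals balance is secured only over both together. That reading rests on one total, one number run and silence about strata; the protocol does not state outright that randomisation is unstratified.

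For assumed shares of 20% to 50%, the 95th-percentile gap in the smaller hospital is 7 to 9 patients, against 2 with a list per hospital. With an assumed 5-point hospital difference this means a shift of about 0.9 to 1.1 points at the 95th percentile, against a standard error of about 3.3. The benefit of changing is a little precision and a more robust-looking result. The sample size is unaffected, and nothing here calls the validity of the trial into question.

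**What to change.** 1. Reconcile section 4 with section 5.3 on where the operations take place, and state the answer in section 5.2.
2. If both hospitals operate, prepare one envelope series per hospital, each with its own number prefix and randomly varying block sizes, with the total capped at 82. Keep the block sizes from the surgeons, which means removing them from section 5.2 and holding them in a document that surgeons do not see.
3. Include hospital as a fixed effect in the primary model. If baseline is one of the modelled time points, let hospital interact with time, since a constant hospital effect cancels out of a change score.
4. If a single list is kept, still include the hospital term, and state how numbers are issued across the two theatres.
5. If hospitals are added later, say in advance how they will be handled. Each new list brings another incomplete block.

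Cost: a second list, a second envelope set and the hospital term. Two downsides should be accepted knowingly: the final split may miss 41:41 by a few patients, with negligible effect on the standard error, and block ends are somewhat easier to predict within a hospital. Stratifying by surgeon as well would make the strata too small at this sample size.

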5.3. Operative procedure

In this study Autologous Chondrocyte Implantation (ACI) is compared with Arthroscopic Debridement (AD). All patients will undergo a diagnostic arthroscopy, and patients randomized to AD will have this procedure performed at the end of the diagnostic arthroscopy, while for the patients in the ACI group the chondrocyte implantation will take place two weeks later in a second stage operation as described below. The ACI technique is based on the technique described by Brittberg [23].

Diagnostic arthroscopy:

Three standard incisions are made (supralateral for the patella and medial and lateral for the patellar tendon). A thorough diagnostic arthroscopic examination is then done. Removal of loose bodies and other necessary intraarticular procedures are done first (meniscus, plica). The focal cartilage lesion is then measured using a standard 4-mm arthroscopic probe and ICRS graded [39, 40].

Then either arthroscopic debridement (AD) or autologous chondrocyte implantation (ACI) is done, depending on randomization.

Autologous Chondrocyte Implantation

ACI is a three stage procedure taking place at Akershus University Hospital and Oslo University Hospital (Ex-Vivo Laboratory) over a two week period.

Stage 1: Debridement and cartilage harvest.

Stage 1 includes a diagnostic arthroscopy with full inspection of the knee joint to ensure the inclusion criteria are fulfilled. Loose bodies are removed, any meniscal pathology is addressed. Inflamed synovium is debrided. The lesion is stabilized by debridement around the edges and down to the subchondral bone using a ring curette, but not through it, as described above. Cartilage biopsy is then taken from the non-weightbearing area of the medial aspect of the femoral notch. If this area does not contain enough healthy cartilage, the secondary donor site will be the non-weight bearing aspect of the lateral femoral condyle. Complications or donor site morbidity following arthroscopic harvesting of cartilage in this manner has not been described [22].

Stage 2: Chondrocyte growth in Ex Vivo Laboratory Rikshospitalet, Oslo University Hospital

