The harvested cartilage is transported to the cell culture laboratory (Ex Vivo Laboratory at OUS, directed by [name]) in a sterile tube containing 0.9 % NaCl. The cells undergo mechanical mincing and antibiotic washing, and isolation of the chondrocytes by overnight collagenase digestion. The chondrocytes are then cultured for two weeks and resuspended to a treatment density of 30 million cells/ml. The cells are then transported back to Ahus for implantation.

Stage 3: Implantation of chondrocytes two weeks after initial arthroscopy.

The chondrocyte implantation is performed under general or spinal anesthesia, and a tourniquet inflated to 300 mmHg to achieve a blood-less field is applied to the upper thigh. A mini-open arthrotomy (medial or lateral depending of the location of the lesion) is performed and the lesion is assessed. The lesion is curetted down to subchondral bone, but care is taken to avoid bleeding. The surrounding cartilage is debrided to healthy tissue, exposing the lesion to bare bone. The lesion is measured and a template of sterile aluminum foil is used to model the exact shape of the lesion, overcorrecting with 1-2 millimeters.

The template is then used to cut out a matching piece of collagen sheet (ChondroGide® (Geistlich Pharma, Switzerland)) which is used to contain the cells in the defect. The flap is sutured to the lesion with 6.0 resorbable stitches and sealed with fibrin glue, leaving an opening at the upper part for injection of the cells. Saline is injected to the cavity to check for leakage, then aspirated before the cells are slowly injected using a soft catheter. The last opening is then closed with a last stitch and fibrin glue. The knee is then closed in the standard manner, taking care to close the capsule with subcutaneous resorbable sutures, before closing the skin incision with nylon sutures.

Arthroscopic Debridement

The AD group will be subjected to a diagnostic arthroscopy with a full inspection of the knee joint to ensure the inclusion criteria are fulfilled. Loose bodies are removed, any meniscal pathology is addressed. Inflamed synovium is debrided. The lesion is stabilized by debridement around the edges and down to the subchondral bone using a ring curette, but not through it. Microfracture or any other cartilage treatment will not be performed.

No intra-articular local anesthetics will be used due to the possible harmful effect on cartilage [41-43].

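### The envelope is opened before the lesion debridement that both arms share, so the surgeon does that step knowing the arm when nothing in the described sequence requires it

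*Protocol*

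**What the plan says.** Eligibility is settled first. Section 5 states: "The definitive inclusion of the patient will be performed by the operating surgeon during the diagnostic arthroscopy, prior to randomization". Section 5.2 places allocation directly after the lesion assessment: "The randomization process occurs in the operation theatre during the arthroscopy after the operating surgeon has measured and graded the lesion".

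Section 5.3 gives the order of the operation. In the shared diagnostic-arthroscopy paragraph, concomitant work comes first: "Removal of loose bodies and other necessary intraarticular procedures are done first (meniscus, plica". Next, "The focal cartilage lesion is then measured using a standard 4-mm arthroscopic probe and ICRS graded". The paragraph ends: "Then either arthroscopic debridement (AD) or autologous chondrocyte implantation (ACI) is done, depending on randomization".

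The arm paragraphs of 5.3 describe the lesion debridement in the same terms. ACI Stage 1 has "The lesion is stabilized by debridement around the edges and down to the subchondral bone using a ring curette, but not through it, as described", and the AD paragraph has "The lesion is stabilized by debridement around the edges and down to the subchondral bone using a ring curette, but not through it". Both also contain the lines "Loose bodies are removed, any meniscal pathology is addressed. Inflamed synovium is debrided". In Stage 1 the cartilage biopsy follows the debridement. In Stage 3, two weeks later, the lesion is curetted again and its rim debrided at an open operation. AD has no second operation.

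**The concern.** Up to the biopsy, the first operation is meant to be the same in both arms. The surgeon nevertheless learns the arm before debriding the lesion. With an AD allocation the surgeon knows that this is the only treatment the lesion will receive. With an ACI allocation the surgeon knows that it will be prepared again at arthrotomy. That knowledge could influence how thoroughly the shared step is done.

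The other safeguards do not cover this step. Section 4 says that patients cannot be blinded, and the primary endpoint in section 6.2, KOOS QoL, is patient-reported. The examiner's blinding and the opaque stocking protect the follow-up assessment, not the delivery of surgery. The protocol also takes debridement seriously as a comparator: section 3.1 cites a trial in which 31% of candidates improved substantially after debridement with physiotherapy and needed no further treatment.

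**Working it through.** The point concerns the order of steps, so the check is to line up sections 5, 5.2 and 5.3.

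| Step | Where described | Position relative to the envelope |
|---|---|---|
| Diagnostic inspection | 5.3, shared paragraph | Before |
| Loose bodies, meniscus, plica | 5.3, shared paragraph (loose bodies and meniscus also in both arm paragraphs) | Before, on the shared text |
| Lesion measured and graded | 5.2; 5.3, shared paragraph | Before |
| Definitive inclusion by the surgeon | 5 | Before |
| **Envelope opened** | 5.2 | n/a |
| Synovial debridement | 5.3, arm paragraphs only | Not fixed |
| Lesion debridement, both arms | 5.3, arm paragraphs | After |
| Cartilage biopsy, ACI only | 5.3, Stage 1 | After |
| Open implantation with repeat curettage, ACI only | 5.3, Stage 3 | After (two weeks later) |

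1. *Is lesion debridement really after allocation?* Yes. Section 5.3 performs AD or ACI according to the allocation once the lesion has been measured. Its opening paragraph also says that patients already randomized to AD have it at the end of the diagnostic arthroscopy. Stage 1 of ACI carries debridement in its title and belongs to the allocated treatment.
2. *Is the step the same in both arms?* Yes, as written: same instrument, same treatment of the edges, same depth limit.
3. *Does anything before the biopsy require the arm to be known?* Nothing in the described sequence does. The biopsy is the first arm-specific act, and it comes after debridement.
4. *Where would a difference matter?* Mainly in AD. Stage 3 prepares the ACI lesion again, so a difference at Stage 1 is largely overtaken there.

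Sample size is not in dispute. With a difference of 10, SD 15, two-sided 5% and 80% power, the normal approximation gives 2 × (1.96 + 0.84)² × 15² / 10² = 2 × 7.84 × 2.25 = 35.3, so 36 per group. The t-test solution is 36.3, so 37, with 80.8% power. Then 37 × 1.10 = 40.7, so 41 per group and 82 in total, as in section 7.3. The timing of the envelope enters none of these figures.

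**The case against.** The strongest reply is that the protocol already controls what it can. Allocation during the operation, after eligibility, measurement and grading, protects against selection. The debridement is specified identically, the AD paragraph rules out any other cartilage treatment, and all surgeons are trained before the study starts. No passage permits unequal debridement. A surgeon who knows that AD is the only treatment has no evident reason to do less. ACI also brings a second operation that no timing of the envelope can conceal.

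Much of this stands. Unequal debridement is a possibility, not something the protocol describes, and its direction is open. The later ACI steps cannot be concealed from the surgeon. But a common technique and training set a standard without concealing the arm, and the shared step is a part of surgical delivery that could be protected.

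A reader might infer more, and the documents do not support it:

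- *That the whole control treatment and the concomitant surgery are done unblinded.* The shared paragraph of 5.3 puts loose-body, meniscal and plica work before measurement, hence before allocation. The arm paragraphs begin again with the inspection that checks eligibility, so they plausibly retell the operation from its start and do not add a second round after allocation.
- *That the 31% in section 3.1 sizes the bias.* It follows debridement plus intensive rehabilitation, with nothing to separate the two, and the same section suggests that rehabilitation may explain the improvement. It says nothing about how thorough the debridement was.
- *That the lesion-severity adjustment in section 7.2 is compromised because lesions are measured again only in ACI.* Section 7.2 names severity of the lesion as a possible adjustment factor and does not propose the arthrotomy measurement.

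**Conclusion.** The point holds in a limited form. The lesion debridement, which all 82 planned patients (41 per arm) are to undergo, is done after the arm is known, although the sequence does not need it to be. This is an avoidable performance-bias risk, chiefly in the AD arm. Its size and direction are unknown: the documents give no figure in KOOS points, and none should be attached to it. A second, smaller point is that the position of synovial debridement relative to the envelope is not fixed, because only the arm paragraphs mention it.

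The conclusion rests on reading sections 5.2 and 5.3 in the order written, and on the biopsy being the first act that depends on the arm. It does not show that the trial will be biased or that its design fails. The change is worth making because it removes a route to bias at almost no cost.

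**What to change.** In sections 5.2 and 5.3, state one order for every patient:

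1. Confirm and record eligibility, lesion size and grade.
2. Complete and record the shared procedures already described, including synovial and lesion debridement.
3. Only then open the envelope, immediately before the biopsy (ACI) or closure (AD).

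Reconcile the shared and arm-specific paragraphs of 5.3 to this order, so that each shared step appears once and its place relative to allocation is explicit. The cross-reference in 5.2 to an operative-procedure section 4.3 should point to 5.3.

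The cost is a change of wording and an envelope opened somewhat later in the same session. It needs no extra staff, procedure or patients, and leaves surgical technique, sample size, alpha and power unchanged.
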